Spectroscopic: For our preliminary data from 7 ASD and 7 HC subjects, our significant finding (paired t-test, p =0.01) of 31% higher Glu levels in the ACC of ASD subjects compared to HCs was determined to have a large effect size of d=1.20 with an associated power= 0.55. Left MTL data produced an effect size d=1.03 with power = 0.43. Right MTL data produced an effect size d=1.15 with power =0.51. Assuming we observe the same sampling variability in the proposed study, we have greater than 90% power with a large effect size of d=1.10 to detect a 15% decrease in Glu in the ASD group with treatment.

Functional: In our preliminary studies (ASD: N=17; HC: N=16) of resting state functional connectivity with the bilateral amygdalae seeds, we found significant hyperconnectivity of the ASD group compared to the HC group (e.g., with the insula, p<0.0001 FWE cluster level corrected), and based on the preliminary data, power will be at 95% to detect between-group differences between the proposed ASD (N=40) and HC groups (N=20).

VII. RISKS AND DISCOMFORTS

Risks of Taking Memantine:

The most frequently observed adverse reactions with memantine are dizziness, confusion, headache, constipation, hypertension, cough, pain, hallucinations, somnolence, vomiting, dyspnea, and fatigue. Serious adverse reactions include Stevens-Johnson syndrome and seizures. All participants will be closely monitored for serious adverse reactions and drug-drug interactions with their ongoing concomitant medications. All serious unexpected adverse experiences of a research subject will be reported to the Partners Human Research Committee.

Problems and side effects not listed above and not known at this time could occur. Subjects will be told of any changes in the way the study will be done and any newly discovered risks to which they may be exposed.

Risks of Blood Draws:

When blood is drawn, some discomfort may be associated with it at the time of the blood draw. Bruising and/or bleeding at the needle site may occur. Occasionally a person feels faint. Rarely, an infection may develop. If an infection does occur, it can be treated. A topical anesthetic cream (Topicaine, EMLA, or ELA-MAX) will be applied to numb the skin where blood will be drawn if subjects prefer.

Risks of ¹HMRS:

¹HMRS is not associated with any known adverse effects except to people with metal or magnetic implants (such as metal clips from surgery or a cardiac pacemaker). Therefore, if a subject has such metal objects in her/his body, s/he will be excluded from participating in the scanning component of the study.

There are no known risks of scanning for fetuses. However, the safety of scans for pregnant women and nursing mothers has not been established. Therefore, subjects must have a negative pregnancy test prior to each scan and nursing mothers cannot participate. If a participant has a positive pregnancy test, the study doctor will inform the subject and she will not be able to take part in the study. The decision whether to inform the parent of these results will be made by the physician based on the participant's age and maturity level and the requirements of the law, unless the participant agrees to parental notification. Birth control will be required for subjects who are sexually active. There may be some risk of emotional distress in the event of a positive pregnancy test.

Risks of Assessments:

Some of the questions asked in this study may make subjects feel uncomfortable, and some of the neuropsychological testing may be boring or frustrating. While we hope subjects and their parents will answer all questions, they may skip any questions they do not wish to answer.

Adverse events and unanticipated problems will be reported to the PHRC according to current guidelines. We will follow and adhere to all guidelines as defined and outlined on the Partners Human Research Committee web site:

(http://healthcare.partners.org/phsirb/adverse_events.htm).

VIII. POTENTIAL BENEFITS

There may be no direct benefit to subjects participating in this study. Potential benefits to the participants include education about ASD, a trial of medication that could be continued after the study, and the opportunity to contribute to medical science and thus help others with the disorder.

All subjects, including healthy controls, may receive up to \$150 for completing both scanning visits (\$75 will be paid per completed scanning visit).

IX. REFERENCES

- 1. Association AP, DSM-5 Sourcebook. Vol. 1. 2013, Washington, DC: American Psychiatric Association.

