Contraindications to MR scanning—braces, metal in the body, participant refusal to scan (e.g., due to severe anxiety or claustrophobia), etc.—are exclusionary for the scanning component of the trial. Subjects are allowed to have a security object (ei. ball or blanket) that is MR-safe and screened, in the scanner to help with possible anxiety they might experience due to the scanning. Healthy control subjects with contraindications to MR scanning will not be eligible to participate in the trial. However, in the event that an ASD subject with MR scanning contraindications otherwise meets all inclusionary criteria and does not meet any additional exclusionary criteria, that subject will be eligible to participate solely in the 12-week randomized-control phase of the study.

V. SOURCE OF SUBJECTS

We propose to enroll up to 60 subjects with ASD and 30 healthy controls for a total of 90 subjects. Up to 60 children and adolescents with ASD who exhibit marked social impairment will be enrolled in order to randomize 40 eligible subjects. In addition, up to

30 children and adolescents with no history of major psychiatric disorders, including ASD, will enroll in order for 20 eligible age-, sex-, & IQ-matched subjects to participate as neuroimaging healthy controls. Subjects will be recruited from the referral pool of existing and new patients at three different MGH sites – the Bressler Program for ASD, the Lurie Center for Autism, & the child psychiatry outpatient clinic – and from the general public by flyers and internet advertisements. Individuals who respond to local advertising will be screened for eligibility first by the study coordinator over the phone using an IRB-approved script prior to enrollment.

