Participating children and adolescents with ASD who meet the eligibility criteria will be randomly assigned to either memantine or placebo for the course of the 12-week RCT. Subjects will be assessed weekly during the titration phase (Weeks 1-4) & during the maintenance phase at midpoint (Week 6), Week 9, & at completion (Week 12/early termination). The same caretaker (a parent/guardian most familiar with the subject's day-to-day behavior) will participate in the assessment of behavioral symptoms at all visits of the treatment phases.

Randomization: The MGH Clinical Trials Pharmacy will prepare the blinded

memantine and placebo capsules for the study. ASD subjects will be randomized to either active memantine or placebo in a 1:1 ratio after they have been determined to meet all eligibility criteria. Randomization lists stratified by gender and racial/ethnic minority status (minority vs. Caucasian) will be generated by the statistician & passed to the investigational pharmacy for assignment.

Washout Period: ASD subjects who are currently being treated with prohibited psychotropic medications as listed in the exclusion criteria must discontinue the use of their medication to be eligible for participation in this study. Medication washout is recommended by our clinicians to participants, their parent/guardian, and current providers – this is done based on a case-by-case assessment, considering the duration on drug, the dose, and the adverse effects associated with the treatment and effects of stopping that medication/treatment. Our office does not take over care for the patient, but remains available during this time period. The washout schedule –which will span two weeks or more -- will be discussed with the participant, their parent/guardian, and current providers. Individuals taking a medication that is effectively and safely treating their symptoms will not be taken off of such medication for the purpose of enrolling in this study.

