Dose Titration Phase (Weeks 1-4): Study medication will be initiated at 2.5 mg/day, will be raised to 5 mg/day on day 4, and will be gradually up-titrated by 5 mg/week to a maximum dose of 20 mg/day. Titration of the study medication will be guided by the (following) forced titration schedule with an option for slower titration or holding at lower dose per clinician judgment. Memantine will be administered in twice daily divided dosages with a total daily dose of \geq 2.5 mg/day.

Study Medication Dosing: Study medication (memantine/placebo) will be titrated to the maximum daily dose during the first 4 weeks of the trial (dose titration phase). Subjects will follow the following forced titration schedule until Week 4 when subjects will be maintained on maximum achieved dose until the end of the trial (dose maintenance phase; Weeks 5-12). During the dose maintenance phase, there will be a one-time option to decrease the dose of the study medication.

Mema	antine Forced	Titration Schedule
Visit	Day	Maximum Total Dose Prescribed (mg/day)
0	1	2.5
	5	5
1	8	10
2	15	15
3	22	20
4	28	Maintained on maximum achieved dose

Primary Outcome Measure of Efficacy: Clinician-rated CGI-Improvement (CGI-I) subscale and the parent-rated SRS-2. Treatment responders will be defined as those who demonstrated improvement of ≥25% on the SRS-2 total raw score *and* a score of 2 or 1 on the CGI-I subscale ("much" or "very much improved").

Secondary Outcome Measures of Efficacy: As with other psychotropic treatment outcomes in this population⁷², response to memantine may not be uniform for all domains of ASD. The response differential will be examined by assessing change in the severity of the subscales of the SRS-2 representing core domains of ASD, change on the ABC-SW subscale, and change on the MGH-ASD-RS (clinician- and informant-rated). The CY-BOCS-PDD⁷³⁻⁷⁴ will be administered to assess change with treatment in the ritualistic behaviors associated with ASD. Change with treatment in the level of adaptive functioning will be assessed by the CBCL. Change in the level of global functioning will be assessed by the parent/guardian-rated SAICA. Considering that features of ADHD, anxiety, & depression are frequently associated with ASD⁴ & there is evidence of memantine's effectiveness in treating ADHD in adults, these symptoms will be assessed by administering the clinician-rated ADHD-SCL, CDRS-R⁷⁹, & CASI-Anx⁸⁰.

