- CGI- ASD- Social Interaction.
- CGI- ASD– Mannerisms.
- CGI- ASD– Social Communication.
- MGH ASD Symptom Checklist (MGH-ASD-SCL): The spectrum of ASD symptoms will be screened by using clinician administered MGH-ASD-SCL. This screening instrument adopted items from DSM-5 diagnostic criteria for ASD and assesses for the individual core domains and associated features of ASD.
- Social Emotional Competence Scale–Clinician Rated (MGH-SEC-S-C): This is a 37item scale that assesses social competence and abilities in relation to ASD on a Likert scale from 0 to 8.

Level of Functioning

• DSM Global Assessment of Functioning Scale (GAF)⁷⁶: a composite rating of an individual's overall level of functioning (1= worst to 100 = best).

Safety

- Adverse Experiences: to record any adverse health events experienced during the study, along with duration, severity, cause, treatment, and outcome.
- Concomitant Medications: to record additional medications taken during the study.

VI. BIOSTATISTICAL ANALYSIS

Clinical Data Analysis

Because this is a RCT following subjects over a short period of time, missing data are not expected to impact our analyses such that standard statistical tests will be employed. Changes in the primary outcome measures of efficacy (CGI-I & SRS-2) within & between study groups over time will be tested with longitudinal generalized estimating equation (GEE) regression models (RM) estimated using STATA 12.0 within the framework of the general linear model (GLM). For binary outcomes, logistic RMs will be fit with the binomial family & the logit link. For count data, Poisson RMs will be fit with the Poission family & the log link, for normally distributed data, linear RMs will be fit with the Gaussian distribution & identity link. Each model will predict outcome scores from treatment group (memantine vs. PBO), study visit (ordinal predictor), & the group by visit interaction, which is our test of efficacy. Secondary outcome measures (ABC-SW, GAF, ADHD-SCL, CY-BOCS-PDD, CDRS-R, CASI-Anx, & SAICA) will be examined using models similar to the primary outcome measures. Changes in the tolerability outcome measurements will be tested using Chi-squared tests. All analyses will be intention to treat (ITT).

Neuroimaging Data Analysis

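### The plan asks whether drug response differs between ASD domains but has no test between domains and no criterion for a differential, so per-scale results cannot support such a claim

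*Combined protocol and SAP*

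**What the plan says.** Section VII, under Secondary Outcome Measures of Efficacy, sets the question: "response to memantine may not be uniform for all domains of ASD". It then says how the question will be approached: "The response differential will be examined by assessing change in the severity of the subscales of the SRS-2 representing core domains of ASD". Two further measures are added for the same purpose: the ABC-SW, and the MGH-ASD-RS in its clinician and informant forms.

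The models are in Clinical Data Analysis, under Biostatistical Analysis. "Each model will predict outcome scores from treatment group (memantine vs. PBO), study visit (ordinal predictor), & the group by visit interaction", and that interaction is the test of efficacy. The outcomes named as secondary there are "Secondary outcome measures (ABC-SW, GAF, ADHD-SCL, CY-BOCS-PDD, CDRS-R, CASI-Anx, & SAICA"; they "will be examined using models similar to the primary outcome measures". The ABC-SW is on that list. The SRS-2 subscales and the MGH-ASD-RS are not.

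No part of the document contains a domain term, a contrast of drug effects between domains, or a rule for declaring that response differs.

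**The concern.** A response differential is a difference between two treatment effects: the drug effect in one domain minus the drug effect in another. A model with arm, visit and arm-by-visit for a single scale estimates one of those effects. Fitting several such models gives several effects and several p-values, but no estimate or standard error for the difference between them.

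If one subscale reaches significance and the next does not, that does not show that the drug works in one domain and not in the other. Where each scale has moderate power, equal true effects will quite often produce that split. At stake is a secondary conclusion about which core features of ASD respond to memantine, a conclusion that could shape the design of later trials.

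**Working it through.** **Inputs from the document.** Enrolment continues "in order to randomize 40 eligible subjects" (Source of Subjects), and "ASD subjects will be randomized to either active memantine or placebo in a 1:1 ratio" (Randomization). That gives 20 per arm. No dropout rate is stated, so none is applied.

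**Significance level.** None is stated. The spectroscopy pilot figures under Power Considerations let it be inferred. For a two-sample t-test with n per group, the noncentrality is d × √(n/2) on 2n − 2 degrees of freedom. Two-sided 5% gives:

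| d | n per group | Recomputed power | Stated |
|---|---|---|---|
| 1.20 | 7 | 0.541 | 0.55 |
| 1.15 | 7 | 0.507 | 0.51 |
| 1.03 | 7 | 0.426 | 0.43 |
| 1.10 | 20 | 0.924 | above 90% |

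For example, "Left MTL data produced an effect size d=1.03 with power = 0.43" agrees with 0.426. One-sided, normal-approximation and paired versions do not fit the three pilot figures. Two-sided 5% is therefore used below. No power figure is stated for any clinical outcome.

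**Power for one scale at 20 v 20**, by the same formula: 34% at d = 0.5, 69% at d = 0.8 and 92% at d = 1.1. A power of 80% needs d = 0.91.

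**Chance of a split result under a uniform effect.** Assumptions, none of them in the document: K = 2, 3 or 5 domains; the same true d in every domain; equal correlation ρ between domains; a t-test at endpoint in place of the GEE term. The quantity is

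P(split) = 1 − P(no domain significant) − P(all domains significant).

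For K = 2, ρ = 0.7, d = 0.5, simulation gives 1 − 0.54 − 0.22 = 0.24. All cells (40,000 simulated trials each), as K = 2 / 3 / 5:

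| ρ | d = 0.5 | d = 0.6 | d = 0.8 |
|---|---|---|---|
| 0.5 | 31 / 46 / 62% | 34 / 51 / 67% | 30 / 44 / 59% |
| 0.7 | 24 / 36 / 48% | 25 / 39 / 52% | 23 / 34 / 46% |
| 0.8 | 19 / 28 / 39% | 21 / 31 / 43% | 18 / 27 / 38% |
| 0.9 | 13 / 20 / 28% | 15 / 22 / 30% | 13 / 19 / 27% |

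The ranges are 13–34%, 19–51% and 27–67%. Separate runs agree to within about two points.

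**Given that at least one domain is significant**, the split share is P(split) / [P(split) + P(all)]. At ρ = 0.7 and d = 0.5 this is 0.24/0.46 = 52% (K = 2), 0.36/0.53 = 68% (K = 3) and 0.48/0.60 = 80% (K = 5). At ρ = 0.9 and d = 0.8 with K = 2 it is 0.13/(0.13 + 0.63) = 17%.

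**With one joint test.** A single test of the K − 1 between-domain contrasts (Hotelling T²) falsely calls a uniform effect domain-specific in 4.6–5.3% of simulated trials, whatever K, ρ and d.

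**Power of that test for two domains.** The difference between two standardised scores has SD √(2(1 − ρ)). A true between-domain difference of 0.5 SD therefore acts as an effect size of 0.5/√(2(1 − ρ)):

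| ρ | √(2(1 − ρ)) | Effective d | Power, 20 v 20 |
|---|---|---|---|
| 0.5 | 1.000 | 0.500 | 34% |
| 0.7 | 0.775 | 0.645 | 51% |
| 0.8 | 0.632 | 0.791 | 68% |

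For a 0.8 SD difference the corresponding figures are 69%, 89% and 97%.

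**The case against.** The plan never says that a significant result on one scale and a non-significant one on another will be read as a differential. A reader might infer that rule, because separate per-scale tests are all the models produce, but the text says only that change will be assessed. A descriptive comparison of effect estimates fits it equally well. This objection stands: the defect is a missing test and criterion, and misreading is a risk rather than a stated intention.

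A reader might also infer that each SRS-2 subscale has its own planned model. That is explicit only for the ABC-SW. The subscales might be meant to follow the primary SRS-2 model, but this is not written. On either reading, nothing compares domains.

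Third, all SRS-2 subscales come from one questionnaire, and the 12-Week RCT section requires the same caretaker throughout treatment. High correlations are therefore plausible, and the lower rows of the table may be nearer the truth. It would be too strong to call a split the expected pattern: it is a minority outcome in every two-domain cell and at most about even with three. With a very large effect (d = 1.1) it becomes less common still.

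Finally, the joint test itself has limited power in 40 subjects, and this is a secondary question. Both are true. They argue for modest claims, and do not make per-scale results an answer to a between-domain question.

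**Conclusion.** The concern holds in this form: the protocol poses a between-domain question, and its clinical analysis contains neither a comparison between domains nor a criterion for a differential. That part rests on the text alone. Neuroimaging Data Analysis does plan an interaction with pairwise follow-up tests for its three-group glutamate comparison; the clinical domains have no counterpart.

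The size of the misreading risk depends on effect size, correlation and number of domains, none of which the document gives. Replacing the GEE arm-by-visit term with an endpoint t-test changes the effective d but not the mechanism. Over the assumed ranges a split under a uniform effect is common, against about 5% false differential calls with a joint test.

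The documents do not support the further inference that the trial will report false domain-specific efficacy. The primary CGI-I and SRS-2 analysis is unaffected. This should be changed before unblinding, but it does not threaten the trial's main conclusion.

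**What to change.** 1. Name the SRS-2 subscales that represent core domains, and state a model for them and for the MGH-ASD-RS.
2. Add one joint model for the SRS-2 subscales, which share a questionnaire and a visit schedule (Table I: screening, Week 6, Week 12). Divide each subscale by its pooled pre-treatment SD, stack the subscales within subject, and fit arm, domain, visit and their interactions. Take the pre-treatment score from the caretaker who rates during treatment, because Study Procedures allows both parents to complete a form at screening.
3. Make the arm-by-domain contrast at Week 12 the basis for any claim of differential response.
4. Report each domain's effect with a confidence interval, labelled descriptive.
5. Keep the ABC-SW and MGH-ASD-RS as supportive, or add them in a sensitivity analysis. They are different instruments, the MGH-ASD-RS has a clinician-rated form, and Table I places their pre-treatment scores at baseline rather than screening.
6. State the power above, and state that a non-significant contrast does not show uniform response.

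Cost: one extra model on data already scheduled, and fewer domain-specific claims. The contrast also depends on the standardising SD. Entry requires an SRS-2 total raw score of at least 85, which restricts the pre-treatment spread, so a second standardisation should be named in advance as a check.

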Aim 3) To characterize neural functional deficits and/or abnormalities in youth with ASD by comparing ASD subjects to healthy control subjects undergoing the same spectroscopic & RsFc imaging with two scans 12 weeks apart.

III. LENGTH OF STUDY

This study may take up to 20 weeks from enrollment (allowing up to eight weeks to schedule and complete the initial screening process and baseline scan). Once subjects have completed the screening process and baseline characterization, subjects eligible for scanning will complete a baseline scan (for ASD subjects, this scan will be pre-treatment). ASD subjects will then begin the 12-week randomized-controlled trial. All subjects eligible for scanning, including healthy controls, will receive a follow-up scan approximately 12 weeks after the baseline scan. For ASD subjects, this scan will take place between the 10th and 12th week of treatment. All subjects will be taking the study medication at the time of the second brain scan. ASD subjects ineligible for scanning may participate in the 12-week randomized-control phase of the trial only.

IV. SUBJECT SELECTION CRITERIA

A. Inclusion Criteria (all participants)

1. Male & female subjects ages 8-18 years (inclusive).

Participants with ASD

- 3. DSM-5 ASD diagnostic criteria as established by clinical diagnostic interview
- 4. At least moderate severity of social impairment as measured by a total raw score of ≥85 on the parent/guardian-completed Social Responsiveness Scale-Second Edition (SRS-2)⁷¹ and a score of ≥4 on the clinician-administered Clinical Global Impression-Severity scale (CGI-S).

Healthy Control Participants

- 3. Age-, sex-, & IQ-matched with ASD participants.
- No Axis I diagnoses as established by the Kiddie Schedule for Affective Disorders and Schizophrenia—Epidemiological Version (K-SADS-E)⁷⁰ & confirmed by clinical diagnostic interview.
- 5. No significant traits of ASD as screened by SRS-2 (raw score <60).

Exclusion Criteria (all participants)

- 1. IQ ≤70 based on the Wechsler Abbreviated Scale of Intelligence-II (WASI-II) Vocabulary and Matrix Reasoning subtests
- 2. Impaired communicative speech
- 3. Subjects currently treated with the following medications (known to impact glutamate levels):
 - a. Lamotrigine
 - b. Amantadine

- c. N-acetylcysteine
- d. D-cycloserine
- 4. Subjects treated with a psychotropic medication not listed above on a dose that has not been stable for at least 4 weeks prior to study baseline.

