If study participation is discontinued due to safety reasons, participants will receive three follow-up visits, giving adequate time for appropriate psychiatric referrals to treaters in their community. If emergent suicidality were to occur during the course of the study, the supervising clinician will then directly assess the level of risk and take the appropriate action (including contacting treatment providers, working on a safety plan, arranging for emergency evaluation via an ER, calling 911, etc.) The clinician will document the actions taken, and it will be noted in the participant's file. Subjects who discontinue due to non-compliance with the protocol will receive a referral to ASD treaters in the area.

¹HMRS Scanning (ASD and Healthy Control Subjects):

All subjects eligible for scanning will complete two scanning sessions at the McLean Imaging Center over the course of the study. For subjects with ASD, the initial scan will take place after evaluation and screening and prior to randomization. ASD participants will have a second scanning session at McLean between the 10th and 12th week of treatment.

Upon signing consent/assent at MGH, healthy control subjects will participate in screening procedures to assess eligibility. Those who meet eligibility criteria and complete screening procedures will participate in two scanning sessions at McLean Imaging Center. The first scanning session will take place after screening procedures are completed at MGH, and the second scanning session will take place approximately 10-12 weeks after the first.

During the first scanning visit, subjects will undergo a urine drug screen to determine recent drug use, and all women of childbearing potential will be asked to undergo a urine pregnancy screen. A breath sample will be obtained to screen for alcohol. These procedures will be repeated when subjects return to complete for their second scanning visit. Additionally, parents/guardians of all eligible subjects will complete the Child Behavior Checklist (CBCL) during the first scanning visit at McLean Imaging Center in order to assess the child's maladaptive emotional and behavioral problems at the time of the scan.

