After the 2D-JPRESS dataset is resolved into a series of one-dimensional spectra where each spectrum is modeled and fitted with GAMMA simulated J-resolved basis sets, Glu levels will be derived from the total integral across the J-series. Glu transverse relaxation time (T2) will be obtained from the raw peak vs. TE decay curve fitted with

Levenberg-Marquardt algorithm using an exponential decay function (for Glu T2) convoluted with a polynomial function (for Glu J-coupling) that will be obtained from the GAMMA simulation run with previously measured spectral parameters. Data quality will be assessed by LCModel calculated Full Width Half Maximum (FWHM), Signal to Noise Ratio (SNR) and Cramer-Rao Lower Bounds (CRLB).

The following brain measures will be examined between groups and withinsubject across time (e.g., pre- versus post-treatment and correlations between the measures of brain activity and clinical features):

1) ¹HMRS measures of brain Glu in:

a) ACC

b) MTL

2) measures of resting state functional connectivity of:

- a) dorsal & ventral ACC with prefrontal cortex including VMPFC;
- b) bilateral amygdala with insula & VMPFC;

c) bilateral hippocampus with posterior cingulate cortex.

Pretest-posttest brain activity differences will be analyzed using linear regression models, where treatment group is the primary predictor and pretest measures of brain activity are covariates. A general linear regression model will evaluate the difference between the treatment groups in posttest brain measures while controlling for each subject's pretest measures of brain activity. This approach is equivalent to analyses of covariance (ANCOVA). We will also test if changes in Glu in memantine and placebo (PBO) responders differ from changes in Glu over time in healthy controls (HCs). This requires a three-group comparison: memantine responders vs. PBO responders vs. HCs. We will use a GLM to compare Glu changes from baseline to endpoint. If the direction and magnitude of change among the three groups are the same, there will be no group by time interaction. If the interaction is significant and responders show greater changes compared to HCs, it will indicate that the changes observed in responders are greater than expected from normal changes in Glu activity. We will do follow-up tests to separately test the interactions for each pair of the three groups analyzed.

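### The second scan is timed from treatment start in ASD subjects but from the first scan in controls, and no limit is set on the gap between baseline scan and Week 0

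*Combined protocol and SAP*

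**What the plan says.** The combined protocol and SAP sets the timing of the second scan in several places.

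- **VII. Study Procedures, ¹HMRS Scanning, ASD subjects:** "ASD participants will have a second scanning session at McLean between the 10th and 12th week of treatment". The first scan comes after screening and before randomization.
- **Same section, healthy controls:** "the second scanning session will take place approximately 10-12 weeks after the first".
- **III. Length of Study:** "All subjects eligible for scanning, including healthy controls, will receive a follow-up scan approximately 12 weeks after the baseline scan". The same paragraph adds: "For ASD subjects, this scan will take place between the 10th and 12th week of treatment".
- **II. Specific Aims, Aim 3:** both groups are described as "undergoing the same spectroscopic & RsFc imaging with two scans 12 weeks apart".
- **Table I, footnote:** the second scan may fall anywhere from Week 10 to Week 12.

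Section III allows up to eight weeks before treatment, covering screening and the baseline scan together, and 20 weeks in all from enrollment. No section gives a maximum time from baseline scan to Week 0.

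VI. Biostatistical Analysis (Neuroimaging Data Analysis) compares Glu change in memantine responders, placebo responders and healthy controls. If the group-by-time interaction is significant and responders change more than controls, "it will indicate that the changes observed in responders are greater than expected from normal changes in Glu activity". That model lists no term for the time between scans.

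**The concern.** Control change can stand for normal change only if both groups are observed over the same length of time. Here the two groups have different starting points: the ASD clock starts at treatment and the control clock at the first scan. Any wait between an ASD subject's baseline scan and Week 0 is added to the ASD interval and has no counterpart in controls. Subjects are 8-18 years old, so maturation, along with any scanner drift, would have longer to act in the ASD group. Part of a responder-control difference in Glu change could then reflect elapsed time rather than response.

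**Working it through.** **Inputs.** ASD second scan: treatment weeks 10-12 (sections III and VII, Table I). Control second scan: about 10-12 weeks after the first (section VII). Stated interval for all: about 12 weeks (section III, Aim 3). Pre-treatment allowance: 8 weeks. Treatment: 12 weeks. Planned Glu effect: 15% decrease, d=1.10 (Power Considerations).

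**1. The plan's own figure.** 8 + 12 = 20 weeks, as section III states. This is time from enrollment to the end of treatment, not time between scans.

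**2. Interval between scans.** Let g be the weeks from baseline scan to Week 0, with g ≥ 0. The ASD interval is g+10 to g+12 weeks; the control interval is 10 to 12. At matching points in the window, ASD exceeds control by g.

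**3. Fit with the stated 12 weeks.** The range g+10 to g+12 contains 12 only if 0 ≤ g ≤ 2. The two timing rules for ASD subjects agree only for gaps up to about two weeks.

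**4. Is g likely to be zero?** Section VII has a neuroradiologist review the anatomical images, and subjects with structural abnormalities are not included. Randomization follows only once all eligibility criteria are met. The image review therefore belongs between scan and randomization, so some gap is likely.

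**5. Which analyses are touched.** Both randomized arms follow one timing rule and are scanned before randomization, so the memantine-placebo ANCOVA is unaffected apart from a possible loss of precision in the baseline covariate. Comparisons at baseline do not involve the interval. What remains is comparison of change with controls.

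**6. Illustration of size.** The documents give no drift rate, so two assumptions are needed: drift is linear, and controls drift by 1% to 5% of Glu over 11 weeks (the middle of 10-12). The excess ASD change is then g/11 of the control change. If the 15% and d=1.10 describe the same quantity, the SD is 15/1.10 = 13.6% of Glu.

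| g (weeks) | ASD interval (weeks) | g/11 | Excess, % of Glu | Excess, SD |
|---|---|---|---|---|
| 0 | 10-12 | 0% | 0 | 0 |
| 1 | 11-13 | 9% | 0.09-0.45 | 0.007-0.033 |
| 2 | 12-14 | 18% | 0.18-0.91 | 0.013-0.067 |
| 4 | 14-16 | 36% | 0.36-1.82 | 0.027-0.133 |

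For scale, the planned effect is 15% of Glu.

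**The case against.** The best defence is that section III already limits the gap in substance. It puts the follow-up scan about 12 weeks after baseline for everyone, places the baseline scan after screening, and has ASD subjects begin the trial next. Read together with the treatment-week rule, that implies a gap of about 0-2 weeks, and intervals of 10-14 against 10-12 weeks largely overlap. The control window is itself only approximate. This largely stands and keeps the likely effect small. It does not supply a limit: section VII, which sites would follow for scheduling, gives each group its own anchor and no maximum gap.

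A second defence is that placebo responders share the ASD timing rule. An interval artefact should then appear in both ASD responder groups and would not by itself separate drug from placebo. That also stands. It leaves the follow-up contrasts of each responder group with controls exposed.

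A reader might infer from the eight-week allowance that ASD intervals run from 10 to 20 weeks, up to 67% longer than in controls (20/12 = 1.67). The documents do not support that as a working range. The eight weeks include the scan itself, and a scan at the end of the allowance leaves g=0. Twenty weeks needs g=8, with screening and scan finished at enrollment and a rescan at Week 12, which contradicts the stated 12 weeks.

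**Conclusion.** The point holds at modest size. The anchors differ, no maximum gap is stated, and a non-zero gap is likely and can only lengthen the ASD interval relative to controls. If section III and Aim 3 are followed, g is about 0-2 weeks and the excess is at most about two weeks. Longer gaps are not explicitly barred.

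The consequence is confined to comparisons of change with healthy controls. Two stronger conclusions might be drawn, and neither is supported: that control change cannot serve as a measure of normal change, since at short gaps the intervals nearly coincide; and that the randomized imaging comparison is biased, since timing is common to both arms. The size of any bias in Glu is unknown, and so is its sign, which depends on the direction of drift. The figures in the table rest on an assumed linear drift of 1-5% over 11 weeks and show only scale. Severity is minor to moderate.

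**What to change.** 1. Reconcile section III, Aim 3 and section VII so that one rule defines the second-scan date in each group.
2. Set a maximum time from baseline scan to Week 0 that agrees with the stated 12 weeks. About 2 weeks is an example; it gives ASD intervals of 10-14 weeks.
3. Schedule control second scans to the same scan-to-scan interval as the ASD group, rather than to a separate 10-12 week window.
4. Record the actual interval in days, and add it as a covariate in a sensitivity analysis of the ASD-control change comparisons.

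Steps 2 and 3 matter most. If interval tracks group, a covariate alone cannot separate the two, least of all in small responder subgroups. No scans are added. The cost is tighter booking of the baseline scan and of control rescans, plus one recorded variable.
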